**Study Day 28 (Visit #5) – Telephone Call**

1. Review interim medical history emphasizing any acute signs or symptoms (including entries on the post vaccination symptom memory aid).
2. Collect concomitant medication information.

**Study Day 56 (Visit #6: Day of second vaccination)**

1. Perform basic history (including concomitant medications) and physical exam (including injection site), emphasizing examination of any acute complaints.
2. Obtain blood for hematology, biochemistry, rheumatoid factor, anti-dsDNA, anti-Na-GST-1 antibody and CMI assays.
3. For females, obtain a urine sample for pregnancy testing. Test must be negative to proceed; a positive test will exclude the volunteer from further vaccinations.
4. Record vital signs.
5. Administer the vaccine.
6. Observe for at least 1 hour after vaccination to evaluate for immediate adverse reactions. During the 1-hour post-immunization wait period, study staff will discuss signs and symptoms of potential AEs, describe proper use of digital thermometers, injection-site reaction measurement tools, and subject symptom diaries.
7. Record vital signs at the end of the 1-hour post-immunization wait period.

**Study Day 59 (Visit #7) – Telephone Call**

1. Review interim medical history emphasizing any acute signs or symptoms (including entries on the post vaccination symptom memory aid).
2. Collect concomitant medication information.

**Study Day 63 (Visit #8)**

1. Perform basic history and physical exam (including injection site), emphasizing examination of any acute complaints.
2. Record vital signs.
3. Review and collect subject post vaccination symptom memory aid.
4. Obtain blood for CMI immunology assays.

**Study Day 70 (Visit #9)**

1. Perform basic history and physical exam (including injection site), emphasizing examination of any acute complaints.
2. Record vital signs.
3. Review and collect subject post vaccination symptom memory aid (if not collected on Day 63 visit).
4. Obtain blood for hematology, biochemistry, rheumatoid factor, anti-dsDNA, anti-Na-GST-1 antibody and CMI assays.

**Study Day 84 (Visit #10) – Telephone Call**

1. Review interim medical history emphasizing any acute signs or symptoms (including entries on the post vaccination symptom memory aid).

2. Collect concomitant medication information.

Study Day 112 (Visit #11: Day of Third Vaccination)

1. Perform basic history (including concomitant medications) and physical exam (including injection site), emphasizing examination of any acute complaints.
2. Obtain blood for hematology, biochemistry, rheumatoid factor, anti-dsDNA, anti-Na-GST-1 antibody and CMI assays.
3. For females, obtain a urine sample for pregnancy testing. Test must be negative to proceed; a positive test will exclude the volunteer from further vaccinations.
4. Record vital signs.
5. Administer the vaccine.
6. Observe for at least 1 hour after vaccination to evaluate for immediate adverse reactions. During the 1-hour post-immunization wait period, study staff will discuss signs and symptoms of potential AEs, describe proper use of digital thermometers, injection-site reaction measurement tools, and subject symptom diaries.
7. Record vital signs at the end of the 1-hour post-immunization wait period.

Study Day 115 (Visit #12) – Telephone Call

1. Review interim medical history emphasizing any acute signs or symptoms (including entries on the post vaccination symptom memory aid).
2. Collect concomitant medication information.

Study Day 119 (Visit #13)

1. Perform basic history and physical exam (including injection site), emphasizing examination of any acute complaints.
2. Record vital signs.
3. Review and collect subject post vaccination symptom memory aid.
4. Obtain blood for CMI assays.

Study Day 126 (Visit #14)

1. Perform basic history and physical exam (including injection site), emphasizing examination of any acute complaints.
2. Record vital signs.
3. Review and collect subject post vaccination symptom memory aid (if not collected during Day 119 visit).
4. Obtain blood for hematology, biochemistry, rheumatoid factor, anti-dsDNA, anti-Na-GST-1 antibody and cellular immunology assays.
5. Obtain fecal sample for parasitological testing.

Study Day 140 (Visit #15: Application of *N. americanus* Larval Inoculum)

1. Verify that Informed Consent was obtained.
2. Verify that all applicable eligibility criteria have been met.
3. Perform abbreviated history (including concomitant medications) and physical exam, focusing on any acute complaints.
4. Obtain blood for hematology, biochemistry, antibody and cellular immunology assays.
5. Obtain a urine sample for pregnancy testing (females only). Pregnancy test must be negative to proceed; a positive test will exclude the volunteer from the receiving the CHHI.

6. Record vital signs (blood pressure, oral temperature, and heart rate).
7. Administer the *N. americanus* Larval Inoculum.
8. Observe for at least 1 hour after application of the *N. americanus* Larval Inoculum to evaluate for immediate adverse reactions. During the 1-hour post-application wait period, study staff will:
  - Discuss signs and symptoms of potential Adverse Events (AEs);
  - Discuss proper use of the digital thermometer, skin reaction measurement tool, and subject post-CHHI symptom memory aid, and;
  - Review procedures for fecal sample collection, storage, and transport to the clinic.
9. At the end of the observation period, remove absorbent pad used to apply the Larval Inoculum and place in a screw-top tube for transport to GWU MITM.

Study Day 143 (Visit #16) – Telephone Call

1. Review interim medical history emphasizing any acute signs or symptoms (including entries on the post vaccination symptom memory aid).
2. Collect concomitant medication information.

Study Day 147 (Visit #17)

1. Perform basic history and physical exam (including larval application site), emphasizing examination of any acute complaints.
2. Record vital signs.
3. Obtain blood for antibody and cellular assays.
4. Review subject post-CHHI symptom memory aid.

Study Day 154 (Visit #18)

1. Perform basic history and physical exam (including larval application site), emphasizing examination of any acute complaints.
2. Record vital signs.
3. Review and collect post-CHHI symptom memory aid.
4. Give subject two weekly post-CHHI symptom memory aids.
5. Obtain blood for hematology, biochemistry, antibody and cellular assays.

Study Day 175 (Visit #19)

1. Perform basic history and physical exam (including larval application site), emphasizing examination of any acute complaints.
2. Record vital signs.
3. Collect prior weeks' weekly symptom memory aids and give a weekly GI symptom memory aid.
4. Obtain blood for hematology, antibody and cellular assays.
5. Obtain fecal sample for parasitological testing.

Study Day 182 (Visit #20)

1. Perform basic history and physical exam, emphasizing examination of any acute complaints.
2. Record vital signs.
3. Collect prior week's weekly GI symptom memory aid and give new weekly GI symptom memory aid.
4. Obtain fecal sample for parasitological testing.

Study Day 189 (Visit #21)

1. Perform basic history and physical exam, emphasizing examination of any acute complaints.
2. Record vital signs.
3. Obtain fecal sample for parasitological testing.
4. Collect prior week's weekly GI symptom memory aid and give new weekly GI symptom memory aid.
5. Obtain blood for hematology, antibody and cellular assays.

Study Day 196 (Visit #22) – Telephone Call

1. Review interim medical history emphasizing any acute signs or symptoms (including entries on the GI symptom memory aid).
2. Collect concomitant medication information.

Study Day 203 (Visit #23)

1. Perform basic history and physical exam, emphasizing examination of any acute complaints.
2. Record vital signs.
3. Obtain fecal sample for parasitological testing.
4. Collect prior week's weekly GI symptom memory aid and give new weekly GI symptom memory aid.
5. Obtain blood for hematology.

Study Day 210 (Visit #24) - Telephone Call

1. Review interim medical history emphasizing any acute signs or symptoms (including entries on the GI symptom memory aid).
2. Collect concomitant medication information.

Study Day 217 (Visit #25)

1. Perform basic history and physical exam, emphasizing examination of any acute complaints.
2. Record vital signs.
3. Obtain fecal sample for parasitological testing.
4. Collect prior weeks' GI symptom memory aids and give two new weekly GI symptom memory aids.
5. Obtain blood for hematology.

Study Day 224 (Visit #26) - Telephone Call

1. Review interim medical history emphasizing any acute signs or symptoms (including entries on the GI symptom memory aid).
2. Collect concomitant medication information.

Study Day 231 (Visit #27)

1. Perform basic history and physical exam, emphasizing examination of any acute complaints.
2. Record vital signs.
3. Obtain fecal sample for parasitological testing.
4. Collect prior weeks' GI symptom memory aids and give two new weekly GI symptom memory aids.

5. Obtain blood for hematology, antibody and cellular assays.

Study Day 238 (Visit #28) - Telephone Call

1. Review interim medical history emphasizing any acute signs or symptoms (including entries on the GI symptom memory aid).
2. Collect concomitant medication information.

Study Day 245 (Visit #29)

1. Perform basic history and physical exam, emphasizing examination of any acute complaints.
2. Record vital signs.
3. Obtain fecal sample for parasitological testing.
4. Collect prior weeks' GI symptom memory aids and give two new weekly GI symptom memory aids.
5. Obtain blood for hematology.

Study Day 252 (Visit #30) – Telephone Call

1. Review interim medical history emphasizing any acute signs or symptoms (including entries on the GI symptom memory aid).
2. Collect concomitant medication information.

Study Day 259 (Visit #31)

1. Perform basic history and physical exam, emphasizing examination of any acute complaints.
2. Record vital signs.
3. Obtain fecal sample for parasitological testing.
4. Collect prior weeks' GI symptom memory aid and give two new weekly GI symptom memory aids.
5. Obtain blood for hematology.

Study Day 266 (Visit #32) – Telephone Call

1. Review interim medical history emphasizing any acute signs or symptoms (including entries on the GI symptom memory aid).
2. Collect concomitant medication information.

Study Day 273 (Visit #33)

1. Perform basic history and physical exam, emphasizing examination of any acute complaints.
2. Record vital signs.
3. Obtain fecal sample for parasitological testing.
4. Collect prior weeks' GI symptom memory aid and give new weekly GI symptom memory aid.

Study Day 280 (Visit #34)

1. Perform basic history and physical exam, emphasizing examination of any acute complaints.
2. Record vital signs.
3. Obtain fecal sample for parasitological testing.
4. Collect prior week's weekly GI symptom memory aid.
5. Obtain blood for hematology, antibody and cellular assays.
6. For females, obtain a urine sample for pregnancy testing. Test must be negative to proceed with albendazole administration.

7. Dispense 3-dose treatment of albendazole 400 mg once a day by mouth.
8. Observe administration of 1st dose of albendazole, and provide 2 remaining doses to subject for at-home use.

Study Day 290 (Visit #35)

1. Obtain fecal sample #1 collected approximately 1 week post-treatment with albendazole, for test of cure.

Study Day 294 (Visit #36)

1. Obtain fecal sample #2 collected approximately 1.5 weeks post-treatment with albendazole, for test of cure.

Study Day 297 (Visit #37)

1. Obtain fecal sample #3 collected approximately 2 weeks post-treatment with albendazole, for test of cure.
2. Obtain blood for antibody and cellular assays.
3. Only for subjects with laboratory evidence of eosinophilia post-CHHI: obtain blood for hematology testing (complete blood count with white blood cell differential).
4. For females, obtain a urine sample for pregnancy testing (follow-up post albendazole treatment).

Study Day 320 (Visit #38)

1. Perform basic history and physical exam (including injection site), emphasizing examination of any acute complaints.
2. Record vital signs.
3. Obtain blood for rheumatoid factor, anti-dsDNA, anti-Na-GST-1 antibody assays.

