This phenomenon has been observed in some clinical studies with CpG ODNs involving use of CpG 7909 as an antineoplastic agent, in which study subjects have developed detectable antibody to double-stranded DNA. These antibodies have generally declined to baseline after cessation of CpG 7909, and have not been associated with other autoimmune phenomenon, and their possible clinical significance is unknown. Subjects in the study described in this protocol will be closely monitored for laboratory evidence (e.g., anti-double stranded DNA antibodies or rheumatoid factor) or clinical signs or symptoms of autoimmunity.

Female subjects will be cautioned of the unknown risk of the Na-GST-1/Alhydrogel® vaccine administered with or without AP 10-701 or CpG 10104, and of hookworm infection (and of the albendazole used to treat hookworm infection) to the fetus. A female of childbearing potential, unless surgically sterile (i.e., bilateral tubal ligation, bilateral oophorectomy, or complete hysterectomy), at least 2 years postmenopausal, practices abstinence, or has a vasectomized partner, must practice effective contraception (including oral, intra/transdermal, intravaginal, or implanted hormonal contraceptives; intrauterine device (IUD); double barrier methods [condom plus foam or spermicide, diaphragm plus foam or spermicide], or the Essure procedure) until documented clearance of hookworm infection following treatment with albendazole. Female subjects will be counseled by a study team member, or referred to the health provider of their choice, for evaluation and institution of an appropriate contraceptive method.

Female subjects will be cautioned of the theoretical risk of albendazole during pregnancy. Per the FDA's categorization of drug risks to a fetus, albendazole is Category C, indicating that animal reproduction studies have shown an adverse effect on the fetus. However, teratogenicity in humans has not been observed, and a study of over 800 women treated with albendazole during the second and third trimesters demonstrated no adverse effects (70). Use in the first trimester, however, is still not recommended, but potential benefits may warrant use of the drug in pregnant women despite potential risks. Albendazole has been shown to cause embryotoxicity and skeletal malformations in pregnant rats and rabbits. Female subjects will be counseled on the potential risks of albendazole use during pregnancy at each weekly visit.

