#### **2.3.2 Precautions Taken to Minimize Risks**

In order to minimize the risk to subjects, all subjects will be monitored closely during their participation in this study. The study vaccines, AP 10-701, and CpG 10104 have been produced according to current Good Manufacturing Practices (GMP). The *N. americanus* larvae that will be used in this study have been produced according to the procedure outlined in the IND for this product. The vaccine products and *N. americanus* larvae will be administered by experienced investigators with drugs and equipment available for the treatment of anaphylaxis and other potential adverse reactions. All vaccine doses will be given by intramuscular injection to minimize injection site reactions such as pain.

Subjects will be monitored throughout their infection for the development of anemia, by means of regular complete blood counts. Any subject who develops significant anemia during the study

that meets one of the halting rules (see **Section 9.5**) will be treated with albendazole for the infection, according to the procedure outlined in **Section 7.7** of the protocol.

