#### **5.3.4 Handling of Withdrawals**

The primary reason for withdrawal from the study will be recorded on the appropriate data collection form. Subjects will be encouraged to complete the Early Termination Visit. The Early Termination Visit procedures are listed in **Section 7.5**. Although subjects are free to withdraw at any time or may be withdrawn by the Principal Investigator or appropriate co-investigator at any time, subjects who receive at least one dose of study vaccine will be encouraged to remain in the study for follow-up safety assessments and collection of venous blood samples for immunogenicity testing and fecal samples for parasitological testing. Every attempt will be made to follow all adverse events, including solicited injection site and systemic reactions, serious adverse events, and new-onset chronic medical conditions ongoing at the time of early withdrawal to resolution.

Subjects who have received *N. americanus* challenge by CHMI who withdraw or are withdrawn before Day 280 post-CHHI and who have not been treated with albendazole for hookworm infection must receive early presumptive treatment for hookworm or else agree to continue be followed until Day 297 (Visit #37) post-CHHI. Subjects who elect to withdraw from the study will not be subjected to additional research portions of the study (research blood collections, fecal collections, etc.) although they will be strongly advised to continue with the safety portions (i.e., fecal testing for hookworm eggs, safety laboratory tests) of the study.

Although subjects are free to withdraw at any time or may be withdrawn by the Principal Investigator or appropriate co-investigator at any time, subjects will be encouraged to remain in this study for safety follow-up assessments (at a minimum, by telephone if not in person) continuing through approximately study Day 140 for subjects who do not receive CHHI, or study Day 189 (approximately 6 weeks post-CHHI) for subjects who receive CHHI. In the latter case, volunteers will be encouraged to remain in the study until Day 189 to ensure that treatment with albendazole is given after the point where the hookworms would have become adult worms, since the medication is not effective against the immature forms of the worm.

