## 7.5 Early Termination Visit

Every attempt will be made to retain subjects once they have been enrolled. However, if for safety reasons, withdrawal of consent, or loss to follow-up, a subject is deemed by the investigators and/or SMC to be not eligible to receive the study product as per protocol, he/she will discontinue vaccinations. Volunteers will be encouraged to continue attending scheduled study visits to be followed for safety. Study subjects who discontinue the vaccinations or study participation early will not be replaced. Withdrawal from the study for any reason will not impact the subject's medical care.

The following activities will be performed at the early termination visit for subjects who withdraw, or are withdrawn or terminated from the study:

- Obtain interim medical history by interview of subjects and note any changes since the previous visit.
- All concomitant medications will be recorded on the appropriate data collection form (if within 28 days of subject's last vaccination or during the CHHI phase of the study).
- Information regarding adverse events/Serious Adverse Events will be assessed and recorded on the appropriate data collection form.
- A targeted physical examination may be performed by a study clinician licensed to make medical diagnoses and listed on the Form FDA 1572 as the Principal Investigator or co-investigator, if indicated based on review of interim medical history.
- Approximately 10 mL of venous blood may be collected for safety labs and performed by the local clinical laboratory (if prior to Visit 15 and if not recently obtained per study schedule).
- Approximately 40 mL of venous blood may be collected for antibody and cellular assays (if prior to Visit 15 and if not recently obtained).

Subjects who have undergone CHHI and who insist upon terminating the study prematurely and prior to completion of Day 197 will be recommended to take albendazole for hookworm infection (400 mg orally for three consecutive days). Follow-up care will be offered regardless of study participation, if so desired by the subject.

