## 7.6 Unscheduled Visit

Unscheduled visits may occur at any time during the study. Procedures conducted at these visits may include any of the procedures detailed in **Appendix A** as appropriate at the discretion of the investigator depending on the nature of the unscheduled visit. Any of the following activities may be performed:

- Review concomitant medications (if prior to 28 days after a study vaccination or between study Days 140 to 297).
- Review solicited adverse events (if prior to 28 days after a study vaccination or between study Days 140 to 280).
- Review serious adverse events and new-onset chronic medical conditions.
- Obtain medical history by interview of subjects and note any changes since the previous visit (if indicated).

- A targeted physical examination may be performed by a study clinician licensed to make medical diagnoses and listed on the Form FDA 1572 as the site principal investigator or sub-investigator, if indicated based on review of medical history.
- Examine study vaccination site (if within 14 days after a study vaccination).
- Approximately 10 mL of venous blood will be collected for safety labs and performed by the study clinical laboratory (if indicated).

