## 7.7 Clearance of Infection

In order to confirm that treatment with albendazole results in cure of experimental hookworm infection, participants will be asked to provide fecal samples 1, 1½ and 2 weeks following treatment (Days 290, 294 and 297), which will be examined for the presence of eggs by microscopy. Three negative samples are required as confirmation of successful treatment. As treatment with even a single dose of albendazole is currently highly effective (20, 71), and as this study is being conducted in a hookworm non-endemic area, cure following a 3-dose course of treatment is expected for all subjects (72). Nevertheless, if eggs are detected in post-treatment fecal samples, the participant will be given a second course of albendazole, with the same procedure for confirmation of successful treatment.

In addition, treatment with albendazole will be offered to any study participant who wishes to withdraw from the study (whether due to the occurrence of adverse events or for personal reasons) prior to study Day 280. In such an instance, the participant will be strongly encouraged to provide post-treatment fecal samples to ensure cure of the infection. Fecal samples at 1 week, 2 weeks and 60 days following albendazole treatment will be requested for subjects who terminate the study early.

If a female becomes pregnant during the course of the study, provisions for treatment of hookworm infection will be offered (i.e., albendazole treatment after the first trimester of pregnancy).

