## 14.6 Study Discontinuation

If the trial is discontinued, subjects who sign the informed consent form, and are randomized and vaccinated will continue to be followed for safety assessments. No further study vaccinations or CHHI will be administered.

In the event that the study is discontinued, all subjects who received CHHI and who have been and who have not been treated for hookworm will be offered albendazole (3 daily oral doses of 400 mg). The subjects will be asked to follow up weekly for 2 weeks to ensure clearance of infection (see **Section 7.7**).

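### Albendazole at Day 280 requires a negative pregnancy test that day; albendazole given earlier requires none, and no test is scheduled between Days 140 and 280

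*Protocol*

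**What the plan says.** **Scheduled course.** Section 7.3, Study Day 280 (Visit #34), has women give urine for a pregnancy test before the three-dose course is dispensed: "Test must be negative to proceed with albendazole administration".

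**Scheduled tests.** Section 7.3 and Appendix A place pregnancy tests at screening and on Days 0, 56, 112, 140, 280 and 297. The Day 297 test follows treatment.

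**Earlier routes to albendazole.**
- Section 2.3.2: a subject with significant anemia that meets a halting rule "will be treated with albendazole for the infection, according to the procedure outlined in" Section 7.7.
- Section 5.3.4: challenged, untreated subjects who leave before Day 280 "must receive early presumptive treatment for hookworm or else agree to continue be followed until Day 297". The same section also has staff treat subjects who missed follow-up and are then located.
- Section 7.7: before Day 280, "treatment with albendazole will be offered to any study participant who wishes to withdraw from the study".
- Section 7.5: challenged subjects who insist on stopping "prior to completion of Day 197 will be recommended to take albendazole for hookworm infection".
- Section 14.6: if the trial is discontinued, challenged and untreated subjects "will be offered albendazole (3 daily oral doses of 400 mg").

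**Pregnancy provisions.** Section 2.3.1.2 states: "Use in the first trimester, however, is still not recommended, but potential benefits may warrant use of the drug in pregnant women". It reports embryotoxicity and skeletal malformations in rats and rabbits, and says that teratogenicity has not been seen in humans. Sections 7.7 and 9.3.6 defer albendazole past the first trimester in a woman who becomes pregnant.

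**The concern.** The protocol sets its own standard. Every scheduled product (three vaccinations, the larval challenge and the Day 280 albendazole) needs a negative pregnancy test on the day. The standard lapses when the same drug is given to the same women on another date.

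The stake is subject safety. An early pregnancy that nobody has recognised could be exposed to albendazole in the trimester when the protocol advises against its use. The deferral rule in 7.7 and 9.3.6 cannot prevent this, because it acts only once the pregnancy is known, and on the off-schedule routes nothing mandatory would reveal it. Symptoms are a weak prompt: nausea, vomiting and bloating are expected effects of the challenge infection.

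**Working it through.** There is no plan figure to reproduce. The check compares the dosing routes, then measures the gap.

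**1. Is a test required before dosing?**

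| Route | Section | Status of albendazole | Test required |
|---|---|---|---|
| Scheduled, Day 280 | 7.3 | given to all challenged subjects, except those entering the donor sub-study (7.8) | yes, same day |
| Significant anemia | 2.3.2, through 7.7 | given | no |
| Withdrawal before Day 280 | 5.3.4, 7.7 | mandatory unless followed to Day 297; offered | no |
| Early termination before completion of Day 197 | 7.5 | recommended | no |
| Study discontinuation | 14.6 | offered | no |

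None of the four off-schedule routes requires a test. The 7.5 activity list covers history, medications, adverse events, examination and blood samples, with no urine test. Treatment of located subjects in 5.3.4 is equally silent.

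**2. Time since the last scheduled test (Day 140), in nominal days**
- Treated by Day 279 under 5.3.4, 7.7 or 14.6: 279 − 140 = 139 days.
- Treated under 7.5, limit Day 197: 197 − 140 = 57 days.
- Treated at Day 189, the point to which 5.3.4 asks challenged leavers to stay: 189 − 140 = 49 days.

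**3. How many women could be affected?** Section 14.4 expects roughly equal numbers of each sex, so about 48 / 2 = 24 women. This is a ceiling for all routes together: some are sterile, abstinent or have a vasectomized partner, and no withdrawal rate is given.

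If the whole study were discontinued on one date, only women between Days 140 and 280 would be in the untested window, which lasts 280 − 140 = 140 days. Assuming uniform enrollment, the largest share in the window is 140 divided by the enrollment period:
- Estimated enrollment time of 6 months (Protocol Summary), about 182 days: 140 / 182 = 77%, and 0.77 × 24 = about 18 women.
- Enrollment implied by study duration less participation, 22 − 14 = 8 months, about 243 days: 140 / 243 = 58%, and 0.58 × 24 = about 14 women.

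These are women who could be offered untested treatment, not women expected to be pregnant. The documents do not allow the latter to be estimated.

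**The case against.** The case against is mainly about consequence. Effective contraception is required until clearance is documented (2.3.1.2, 5.2). The risk is counselled at each weekly visit. Memory aids carry a printed warning and record the contraceptive in use (9.2.3), and subjects are in weekly contact from Day 175. Anemia that meets a halting rule goes to safety review (9.5). Section 7.6 allows any Appendix A procedure at an unscheduled visit "at the discretion of the investigator depending on the nature of the unscheduled visit", so a clinician may test. Section 9.3.6 shows that pregnancy between challenge and Day 280 was considered.

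All of this stands as mitigation and limits the seriousness. It does not close the gap: women under the same safeguards must still test negative at Day 280, and permission to test is not a requirement.

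The counts can also be called high. Section 5.3.4 notes that albendazole does not work on immature worms. If treatment after discontinuation waited until Day 189, the window would be 280 − 189 = 91 days, giving 91 / 182 = 50% (about 12 women) or 91 / 243 = 37% (about 9). That is a fair lower scenario, but 14.6 sets no such timing, so the larger figures remain valid ceilings. It is also true that 139 days is time since a test, not time for which a pregnancy would plausibly go unnoticed.

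Finally, an absolute test requirement needs a rule for a woman who leaves and declines testing. That is a drafting point; the Day 280 requirement has no such rule either.

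**Conclusion.** The concern holds. The same-day negative test required at Day 280 is required on none of the off-schedule routes, and no test is scheduled between Day 140 and Day 280. The interval since the last scheduled test can reach 139 days, or about 57 days under 7.5. This is an omission, not a prohibition on testing.

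The ceiling is about 24 women over all routes, and about 14 to 18 at a single discontinuation date, assuming half the subjects are women and enrollment is uniform. The number treated early is probably far smaller. The Manual of Procedures and the consent form were not available and might add a test, but a precondition for dosing that the protocol states for Day 280 belongs in the protocol for every other course. The change should be made on safety grounds.

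**What to change.** State the rule once, in Section 7.7: before any albendazole course, scheduled or not, a female subject must have a negative urine pregnancy test on the same day, and a positive result is managed under Section 9.3.6. Worded this way, it also covers located subjects (5.3.4) and a second course after failed cure (7.7). Then:
- cross-reference the rule in 2.3.2, 5.3.4 and 14.6;
- add the urine test to the 7.5 activity list;
- footnote the Appendix A pregnancy-test row to show a test before any off-schedule albendazole;
- preferably, say how a refusal of testing is handled.

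The cost is protocol wording and one urine test per woman treated off schedule, with kits the site already uses. Design, sample size and analysis are unchanged.
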